## 8.2 Appendix 2: European Network of Centres for Pharmacoepidemiology and Pharmacovigilance Checklist for Study Protocols

**Study title:** A multi-country, non-interventional, cohort study to evaluate the effectiveness of OM-85 for the prevention of recurrent respiratory tract infections in paediatric and adult patients, and its use in routine clinical practice

**EMA-HMA Catalogue number:** Not yet available  
**Study Reference Number (If Applicable):** Not yet available

Section 1: Milestones	Yes	No	N/A	Section Number
1.1 Does the protocol specify timelines for				-
1.1.1 Start of data collection 				
1.1.2 End of data collection 				
1.1.3 Progress report(s)				
1.1.4 Interim report(s)				
1.1.5 Registration in the EMA-HMA catalogue				
1.1.6 Final report of study results				

Comments:

Section 2: Research question	Yes	No	N/A	Section Number
2.1 Does the formulation of the research question and objectives clearly explain:				2
2.1.1 Why the study is conducted? (e.g. to address an important public health concern, a risk identified in the risk management plan, an emerging safety issue)				1.2
2.1.2 The objective(s) of the study?				2
2.1.3 The target population? (i.e. population or subgroup to whom the study results are intended to be generalised)				2
2.1.4 Which hypothesis(-es) is (are) to be tested?				-
2.1.5 If applicable, that there is no a priori hypothesis?				-

Comments:

 Date from which information on the first study is first recorded in the study dataset or, in the case of secondary use of data, the date from which data extraction starts.

 Date from which the analytical dataset is completely available.

Section 3: Study design		Yes	No	N/A	Section Number
3.1	Is the study design described? (e.g. cohort, case-control, cross-sectional, other design)				3.1
3.2	Does the protocol specify whether the study is based on primary, secondary or combined data collection?				3.1
3.3	Does the protocol specify measures of occurrence? (e.g., rate, risk, prevalence)				3.3.2
3.4	Does the protocol specify measure(s) of association? (e.g. risk, odds ratio, excess risk, rate ratio, hazard ratio, risk/rate difference, number needed to harm (NNH))				3.7
3.5	Does the protocol describe the approach for the collection and reporting of adverse events/adverse reactions? (e.g., adverse events that will not be collected in case of primary data collection)				5

Comments:

Section 4: Source and study populations		Yes	No	N/A	Section Number
4.1	Is the source population described?				3.2.2
4.2	Is the planned study population defined in terms of:				
	4.2.1 Study time period				3.2.1
	4.2.2 Age and sex				3.2.2
	4.2.3 Country of origin				3.2.1
	4.2.4 Disease/indication				3.2.2
	4.2.5 Duration of follow-up				3.2.1
4.3	Does the protocol define how the study population will be sampled from the source population? (e.g. event or inclusion/exclusion criteria)				3.2.2

Comments:

4.2.2: The study population, in terms of eligibility criteria, is not defined based on sex. However, sex is used as a covariate, including as a PS matching variable.

Section 5: Exposure definition and measurement		Yes	No	N/A	Section Number
5.1	Does the protocol describe how the study exposure is defined and measured? (e.g. operational details for defining and categorising exposure, measurement of dose and duration of drug exposure)				3.3.1
5.2	Does the protocol address the validity of the exposure measurement? (e.g. precision, accuracy, use of validation sub-study)				3.9.2.1
5.3	Is exposure categorised according to time windows?				3.3.1.2 / 3.3.2.2

Section 5: Exposure definition and measurement	Yes	No	N/A	Section Number
5.4 Is intensity of exposure addressed? (e.g. dose, duration)				3.3.1.2
5.5 Is exposure categorised based on biological mechanism of action and taking into account the pharmacokinetics and pharmacodynamics of the drug?				3.3.1 / 3.3.2.2
5.6 Is (are) (an) appropriate comparator(s) identified?				3.3.1.1

Comments:

5.3: The secondary objective 2 explores the OM-85 exposure patterns based on duration of treatment cycles, which can be used in the interpretation of the comparative results.
5.5: The biological mechanism of action is considered in the construction of the follow-up time, as the exposure is considered static, and not censored when patients end taking daily doses. Additionally, as mentioned above, the secondary objective 2 explores the OM-85 exposure patterns.

Section 6: Outcome definition and measurement	Yes	No	N/A	Section Number
6.1 Does the protocol specify the primary and secondary (if applicable) outcome(s) to be investigated?				3.3.2
6.2 Does the protocol describe how the outcomes are defined and measured?				3.3.2
6.3 Does the protocol address the validity of outcome measurement? (e.g. precision, accuracy, sensitivity, specificity, positive predictive value, use of validation sub-study)				3.3.2/ 3.7.8/ 3.9.2.2
6.4 Does the protocol describe specific outcomes relevant for Health Technology Assessment? (e.g. HRQoL, QALYs, DALYS, healthcare services utilisation, burden of disease or treatment, compliance, disease management)				-

Comments:

6.3: While no formal validation study is conducted, the primary outcome definition has been designed with clinicians and the main definition is assessed for robustness in Step 1 of the analyses and as part of the sensitivity analyses.
--------------------------------------------------------------------------------------------------------------------------------------------------------------------------------------------------------------------------------------------

Section 7: Bias	Yes	No	N/A	Section Number
7.1 Does the protocol address ways to measure confounding? (e.g. confounding by indication)				3.3.3/ 3.7.1/ 3.9.1
7.2 Does the protocol address selection bias? (e.g. healthy-user/adherer bias)				3.1.1/ 3.9.3
7.3 Does the protocol address information bias? (e.g. misclassification of exposure and outcomes, time-related bias)				3.9.2 / 3.9.4

Comments:

--

Section 8: Effect measure modification	Yes	No	N/A	Section Number
8.1 Does the protocol address effect modifiers? (e.g. collection of data on known effect modifiers, subgroup analyses, anticipated direction of effect)				3.2.2.3

Comments:

--

Section 9: Data Sources	Yes	No	N/A	Section Number
9.1 Does the protocol describe the data source(s) used in the study for the ascertainment of:				
9.1.1 Exposure? (e.g. pharmacy dispensing, general practice prescribing, claims data, self-report, face-to-face interview)				3.3 / 3.4
9.1.2 Outcomes? (e.g. clinical records, laboratory markers or values, claims data, self-report, patient interview including scales and questionnaires, vital statistics)				3.3 / 3.4
9.1.3 Covariates and other characteristics?				3.3 / 3.4
9.2 Does the protocol describe the information available from the data source(s) on:				
9.2.1 Exposure? (e.g. date of dispensing, drug quantity, dose, number of days of supply prescription, daily dosage, prescriber)				3.3 / 3.4
9.2.2 Outcomes? (e.g. date of occurrence, multiple event, severity measures related to event)				3.3 / 3.4
9.2.3 Covariates and other characteristics? (e.g. age, sex, clinical and drug use history, co-morbidity, comedications, lifestyle)				3.3 / 3.4
9.3 Is a coding system described for:				
9.3.1 Exposure? (e.g. WHO Drug Dictionary, Anatomical Therapeutic Chemical (ATC) Classification System)				3.3
9.3.2 Outcomes? (e.g. International Classification of Diseases (ICD), Medical Dictionary for Regulatory Activities (MedDRA))				3.3
9.3.3 Covariates and other characteristics?				3.3
9.4 Is a linkage method between data sources described? (e.g. based on a unique identifier or other)				-

Comments:

--

Section 10: Analysis plan	Yes	No	N/A	Section Number
10.1 Are the statistical methods and the reason for their choice described?				3.7
10.2 Is study size and/or statistical precision estimated?				3.5
10.3 Are descriptive analyses included?				3.7
10.4 Are stratified analyses included?				3.2.2.3 / 3.7.6

Section 10: Analysis plan	Yes	No	N/A	Section Number
10.5 Does the plan describe methods for analytic control of confounding?				3.7.1
10.6 Does the plan describe methods for analytic control of outcome misclassification?				3.9.2.2
10.7 Does the plan describe methods for handling missing data?				3.7
10.8 Are relevant sensitivity analyses described?				3.7.7

Comments:

10.6: While analytic control of outcome misclassification is included in the protocol, the main definition for the primary outcome is assessed for robustness in Step 1 of the analyses and as part of the sensitivity analyses.
----------------------------------------------------------------------------------------------------------------------------------------------------------------------------------------------------------------------------------

Section 11: Data management and quality control	Yes	No	N/A	Section Number
11.1 Does the protocol provide information on data storage? (e.g. software and IT environment, database maintenance and anti-fraud protection, archiving)				3.6.2
11.2 Are methods of quality assurance described?				3.8
11.3 Is there a system in place for independent review of study results?				-

Comments:

11.3: While no independent review of study results is in place, the study steering committee will review the results and provide scientific and clinical guidance on interpretations.
---------------------------------------------------------------------------------------------------------------------------------------------------------------------------------------

Section 12: Limitations	Yes	No	N/A	Section Number
12.1 Does the protocol discuss the impact on the study results of:				
12.1.1 Selection bias?				3.9.3
12.1.2 Information bias?				3.9.2
12.1.3 Residual/unmeasured confounding? (e.g. anticipated direction and magnitude of such biases, validation sub-study, use of validation and external data, analytical methods).				3.9.1
12.2 Does the protocol discuss study feasibility? (e.g. study size, anticipated exposure uptake, duration of follow-up in a cohort study, patient recruitment, precision of the estimates)				3.1.1 / 3.2 / 3.3 / 3.4 / 3.5

Comments:

--

Section 13: Ethical/data protection issues	Yes	No	N/A	Section Number
13.1 Have requirements of Ethics Committee/ Institutional Review Board been described?				4.1
13.2 Has any outcome of an ethical review procedure been addressed?				-
13.3 Have data protection requirements been described?				3.2.2.3 / 3.6.1

Comments:

Section 14: Amendments and deviations	Yes	No	N/A	Section Number
14.1 Does the protocol include a section to document amendments and deviations?				AMENDMENTS AND UPDATES

Comments:

Section 15: Plans for communication of study results	Yes	No	N/A	Section Number
15.1 Are plans described for communicating study results (e.g. to regulatory authorities)?				6
15.2 Are plans described for disseminating study results externally, including publication?				6

Comments:

Name of the main author of the protocol: \_\_\_\_\_

Date: dd/Month/year

Signature: \_\_\_\_\_

### 8.3 Appendix 3: International Classification of Disease Codes

**Table 10 List of International Statistical Classification of Diseases and Related Health Problems 10th Revision Codes**

Variables: Label For Diseases Used In The Study	ICD-10 Code	ICD-10 Code Label Used in the Study
Respiratory Tract Infections (RTIs) – inclusion criterion, primary endpoint and covariate		
All ICD-10 codes for both upper and lower RTIs will be used to define any RTI		
Upper respiratory tract infections, Upper RTIs (URTIs)		
CCI [REDACTED]	PPD	CCI [REDACTED]
CCI [REDACTED]	PPD	CCI [REDACTED]
CCI [REDACTED]	PPD	CCI [REDACTED]
CCI [REDACTED]	PPD	CCI [REDACTED]
CCI [REDACTED]	PPD	CCI [REDACTED] CCI [REDACTED]
CCI [REDACTED]	PPD	CCI [REDACTED] CCI [REDACTED] CCI [REDACTED]
CCI [REDACTED]	PPD	CCI [REDACTED] CCI [REDACTED] CCI [REDACTED]
CCI [REDACTED]	PPD	CCI [REDACTED]
	PPD	CCI [REDACTED]
	PPD	CCI [REDACTED]
	PPD	CCI [REDACTED] CCI [REDACTED]
	PPD	CCI [REDACTED] CCI [REDACTED]
	PPD	CCI [REDACTED] CCI [REDACTED]
	PPD	CCI [REDACTED]
	PPD	CCI [REDACTED] CCI [REDACTED]
	PPD	CCI [REDACTED]
	PPD	CCI [REDACTED]
CCI [REDACTED]	PPD	CCI [REDACTED] CCI [REDACTED]
	PPD	CCI [REDACTED] CCI [REDACTED] CCI [REDACTED]
	PPD	CCI [REDACTED]
CCI [REDACTED]	PPD	CCI [REDACTED]

Variables: Label For Diseases Used In The Study	ICD-10 Code	ICD-10 Code Label Used in the Study
CCI [REDACTED]	PPD	CCI [REDACTED] CCI [REDACTED] CCI [REDACTED]
CCI [REDACTED]	PPD	CCI [REDACTED]
CCI [REDACTED]	PPD	CCI [REDACTED] CCI [REDACTED]
	PPD	CCI [REDACTED]
	PPD	CCI [REDACTED]
Lower respiratory tract infections, lower RTIs (LRTIs)		
CCI [REDACTED]	PPD	CCI [REDACTED]
CCI [REDACTED]	PPD	CCI [REDACTED] CCI [REDACTED]
	PPD	CCI [REDACTED]
	PPD	CCI [REDACTED] CCI [REDACTED]
	PPD	CCI [REDACTED] CCI [REDACTED]
	PPD	CCI [REDACTED] CCI [REDACTED]
	PPD	CCI [REDACTED] CCI [REDACTED] CCI [REDACTED]
	PPD	CCI [REDACTED] CCI [REDACTED]
	PPD	CCI [REDACTED] CCI [REDACTED]
	PPD	CCI [REDACTED] CCI [REDACTED]
PPD	PPD	CCI [REDACTED] CCI [REDACTED] CCI [REDACTED]
	PPD	CCI [REDACTED] CCI [REDACTED]
	PPD	CCI [REDACTED] CCI [REDACTED]
CCI [REDACTED]	PPD	CCI [REDACTED]
CCI [REDACTED]	PPD	CCI [REDACTED] CCI [REDACTED]
CCI [REDACTED]	PPD	CCI [REDACTED] CCI [REDACTED]
CCI [REDACTED]	PPD	CCI [REDACTED]
Other RTIs: Respiratory tract infections not classified as upper or lower		
CCI [REDACTED]	PPD	CCI [REDACTED] CCI [REDACTED] CCI [REDACTED]
CCI [REDACTED]	PPD	CCI [REDACTED] CCI [REDACTED]

Variables: Label For Diseases Used In The Study	ICD-10 Code	ICD-10 Code Label Used in the Study
CCI [REDACTED]	PPD	CCI [REDACTED] CCI [REDACTED]
CCI [REDACTED]	PPD	CCI [REDACTED] CCI [REDACTED]
Infection-related complications		
Whooping cough	A37	Whooping cough
Scarlet fever	A38	Scarlet Fever
Meningococcal infection	A39	Meningococcal infection
Streptococcal sepsis	A40	Streptococcal sepsis
Other sepsis	A41	Other Sepsis
Other Bacterial diseases, not elsewhere classified	A48	Other Bacterial diseases, not elsewhere classified
Bacterial infection of unspecified site	A49	Bacterial infection of unspecified site
Streptococcus, Staphylococcus, and Enterococcus as the cause of diseases classified elsewhere	B95	Streptococcus, Staphylococcus, and Enterococcus as the cause of diseases classified elsewhere
Other bacterial agents as the cause of diseases classified elsewhere	B96	Other bacterial agents as the cause of diseases classified elsewhere
Bacterial meningitis, not elsewhere classified	G00	Bacterial meningitis, not elsewhere classified
Meningitis in bacterial diseases classified elsewhere	G01	Meningitis in bacterial diseases classified elsewhere
Encephalitis, myelitis and encephalomyelitis	G04	Encephalitis, myelitis and encephalomyelitis
Eustachian salpingitis and obstruction	H68	Eustachian salpingitis and obstruction
Mastoiditis and related conditions	H70	Mastoiditis and related conditions
Cholesteatoma of middle ear	H71	Cholesteatoma of middle ear
Perforation of tympanic membrane	H72	Perforation of tympanic membrane
Rheumatic fever without mention of heart involvement	I00	Rheumatic fever without mention of heart involvement
Rheumatic fever with heart involvement	I01	Rheumatic fever with heart involvement
Rheumatic chorea	I02	Rheumatic chorea

Variables: Label For Diseases Used In The Study	ICD-10 Code	ICD-10 Code Label Used in the Study
Acute and subacute infective endocarditis	I33	Acute and subacute infective endocarditis
Endocarditis and heart valve disorders in diseases classified elsewhere	I39	Endocarditis and heart valve disorders in diseases classified elsewhere
Pneumonia due to Streptococcus pneumoniae	J13	Pneumonia due to Streptococcus pneumoniae
Pneumonia due to Haemophilus influenzae	J14	Pneumonia due to Haemophilus influenzae
Bacterial pneumonia, not elsewhere classified	J15	Bacterial pneumonia, not elsewhere classified
Pneumonia due to other infectious organisms, not elsewhere classified	J16	Pneumonia due to other infectious organisms, not elsewhere classified
Pneumonia in diseases classified elsewhere	J17	Pneumonia in diseases classified elsewhere
Pneumonia, organism unspecified	J18	Pneumonia, organism unspecified
Acute bronchitis	J20	Acute bronchitis
Acute bronchiolitis	J21	Acute bronchiolitis
Unspecified acute lower respiratory infection	J22	Unspecified acute lower respiratory infection
Peritonsillar abscess	J36	Peritonsillar abscess
Bronchitis, not specified as acute or chronic	J40	Bronchitis, not specified as acute or chronic
Simple and mucopurulent chronic bronchitis	J41	Simple and mucopurulent chronic bronchitis
Unspecified chronic bronchitis	J42	Unspecified chronic bronchitis
Abscess of lung and mediastinum	J85	Abscess of lung and mediastinum
Pyothorax with fistula	J86	Pyothorax with fistula
Chronic Obstructive Pulmonary Disease (COPD), including chronic bronchitis (CB)		
Bronchitis	J40	Bronchitis, not specified as acute or chronic
Simple and mucopurulent chronic bronchitis	J41	Simple and mucopurulent chronic bronchitis
Unspecified chronic bronchitis	J42	Unspecified chronic bronchitis
Emphysema	J43	Emphysema
Other chronic obstructive pulmonary disease; including chronic bronchitis (CB)	J44	Other chronic obstructive pulmonary disease

Variables: Label For Diseases Used In The Study	ICD-10 Code	ICD-10 Code Label Used in the Study
Chronic obstructive pulmonary disease exacerbations	See algorithm below	See algorithm below
Chronic lung disease		
Chronic respiratory disease originating in the perinatal period	P27	Chronic respiratory disease originating in the perinatal period
Wilson-Mikity syndrome	P27.0	Wilson-Mikity syndrome
Cystic fibrosis	E84	Cystic fibrosis
Cystic fibrosis with pulmonary manifestations	E84.0	Cystic fibrosis with pulmonary manifestations
Other pulmonary heart diseases	I27	Other pulmonary heart diseases
Coal-worker pneumoconiosis	J60	Coal-worker pneumoconiosis
Pneumoconiosis due to asbestos and other mineral fibres	J61	Pneumoconiosis due to asbestos and other mineral fibres
Pneumoconiosis due to dust containing silica	J62	Pneumoconiosis due to dust containing silica
Pneumoconiosis due to other inorganic dusts	J63	Pneumoconiosis due to other inorganic dusts
Hypersensitivity pneumonitis due to organic dust	J67	Hypersensitivity pneumonitis due to organic dust
Asthma		
Asthma	J45	Asthma
Severe asthma	J46	Status asthmaticus
Asthma exacerbation		
Mild intermittent asthma with (acute) exacerbation	J45.21	Mild intermittent asthma with (acute) exacerbation
Mild persistent asthma with (acute) exacerbation	J45.31	Mild persistent asthma with (acute) exacerbation
Moderate persistent asthma with (acute) exacerbation	J45.41	Moderate persistent asthma with (acute) exacerbation
Severe persistent asthma with (acute) exacerbation	J45.51	Severe persistent asthma with (acute) exacerbation
Unspecified asthma with (acute) exacerbation	J45.91	Unspecified asthma with (acute) exacerbation
Immunocompromised conditions, please see diagnoses used in the definition in Section 8.7		
Kidney diseases		
Essential hypertension	I10	Essential (primary) hypertension

Variables: Label For Diseases Used In The Study	ICD-10 Code	ICD-10 Code Label Used in the Study
Hypertensive heart disease	I11	Hypertensive heart disease
Hypertensive renal disease	I12	Hypertensive renal disease
Hypertensive heart and renal disease	I13	Hypertensive heart and renal disease
Secondary hypertension	I15	Secondary hypertension
Unspecified contracted kidney	N26	Unspecified contracted kidney
Liver diseases		
Alcoholic liver disease	K70	Alcoholic liver disease
Toxic liver disease	K71	Toxic liver disease
Hepatic failure, not elsewhere classified	K72	Hepatic failure, not elsewhere classified
Chronic hepatitis, not elsewhere classified	K73	Chronic hepatitis, not elsewhere classified
Fibrosis and cirrhosis of liver	K74	Fibrosis and cirrhosis of liver
Other inflammatory liver diseases	K75	Other inflammatory liver diseases
Other diseases of liver	K76	Other diseases of liver
Liver disorders in diseases classified elsewhere	K77	Liver disorders in diseases classified elsewhere
Cancer		
Malignant neoplasms	C00 – C97	Malignant neoplasms
In situ neoplasms	D00 – D09	In situ neoplasms
Benign neoplasms	D10 – D36	Benign neoplasms
Neoplasms of uncertain or unknown behaviour	D37 – D48	Neoplasms of uncertain or unknown behaviour
Malnutrition		
Malnutrition	E40 – E46	Malnutrition
Food allergy		
Anaphylactic shock due to adverse food reaction	T78.0	Anaphylactic shock due to adverse food reaction
Other adverse food reactions, not elsewhere classified	T78.1	Other adverse food reactions, not elsewhere classified
Congenital malformations of the respiratory tract		
Congenital malformation of nose	Q30	Congenital malformation of nose

Variables: Label For Diseases Used In The Study	ICD-10 Code	ICD-10 Code Label Used in the Study
Congenital malformation of larynx	Q31	Congenital malformation of larynx
Congenital malformation of trachea and bronchus	Q32	Congenital malformation of trachea and bronchus
Congenital malformation of lung	Q33	Congenital malformation of lung
Congenital malformation of respiratory system	Q34	Congenital malformation of respiratory system
Ischaemic stroke		
Ischaemic stroke	I63	Cerebral infarction
Heart failure		
Heart failure	I50	Heart failure
Atrial fibrillation		
Atrial fibrillation	I48	Atrial fibrillation and flutter
Myocardial infarction		
Myocardial infarction	I21	Acute myocardial infarction
	I22	Subsequent myocardial infarction
	I25	Chronic ischaemic heart disease
Coronary heart disease		
Coronary heart disease	I25	Chronic ischaemic heart disease
Diabetes		
Diabetes	E10 - E14	Diabetes mellitus
Gastro-oesophageal reflux disease		
Gastro-oesophageal reflux disease	K21	Gastro-oesophageal reflux disease
Allergic rhinitis		
Allergic rhinitis	J30	Vasomotor and allergic rhinitis
Atopic dermatitis		
Atopic dermatitis	L20	Atopic dermatitis
Variables used exclusively for subgroups		
Pregnancy (patients who were pregnant)		
Ongoing pregnancy (not yet delivered)	Z32.1	Pregnancy confirmed
	Z33	Pregnant state
	Z34	Supervision of normal pregnancy

Variables: Label For Diseases Used In The Study	ICD-10 Code	ICD-10 Code Label Used in the Study
	Z35	Supervision of high-risk pregnancy
	Z36	Antenatal screening
Delivery	Z37	Outcome of delivery
	Z38	Liveborn infants according to place of birth
Abortion	O03	Spontaneous abortion
	O04	Medical abortion
	O05	Other abortion
	O06	Unspecified abortion

Note: ICD: International Statistical Classification of Diseases and Related Health Problems; SAP: statistical analysis plan; RTI: Respiratory Tract Infection: URTI: Upper RTI; LRTI: Lower RTI; COPD: Chronic Obstructive Pulmonary Disease; CB: Chronic Bronchitis

ICD-9 codes will be provided in the SAP.

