## AMENDMENTS AND UPDATES

The protocol version 1.0 was finalised on 12 September 2024. Due to the comments received in development of the SAP, the protocol was amended as version 2.0.

Number	Date	Section of study protocol	Amendment or update	Reason
1.0	12 Sep 2024	Original document		
2.0	22 Nov 2024	Sections 3.1, 3.2, 3.3, 3.7, 3.9	1. Using propensity score match only as the main analysis with beginning of follow-up starting at the end of the initiation grace period. The clone censor weighting was included as sensitivity analysis.	1. The clone censor weighting and propensity score matching simultaneously was considered redundant and unnecessary.
		Throughout protocol	2. For clarification >1 RTI during baseline has been updated to $\geq 1$ RTI during baseline, which would make the CED the 2 nd , 3 rd ...n th RTI episode.	2. In reviewing the protocol, there was some confusion regarding the number of RTI episodes during baseline for inclusion criteria and how that corresponds to the number RTI episode that is the CED event. Language has been updated for clarification.
		Throughout protocol	3. For objectives where COPD, CB and asthma exacerbations will be examined, it has been clarified that it is COPD/CB and asthma separately in patients with prior corresponding exacerbations	3. To improve clarity of the objective, wording of the objective has been updated.
		3.2.2.3- Table 5	4. Update age in subpopulations to be $\geq 65$ years and $\geq 80$ years in place of >65 and >80 years	4. To be aligned with the subgroups for age at CED, age groups for subpopulations have been updated.
		Appendix 3	5. Update ICD-10 codes for asthma exacerbation and codes of component conditions in COPD exacerbation	5. In further review of the ICD codes in Appendix 3, additional codes have been found to clarify and expand the definition of asthma exacerbation and some minor modifications to ICD codes in COPD exacerbation, since it was adapted from definitions originally created in ICD-9.

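### Table 10 lists J46 (status asthmaticus) only as background asthma, so on the visible code list an attack coded J46 alone does not count as an asthma exacerbation

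*Protocol*

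**What the plan says.** Protocol Section 8.3 (Appendix 3), Table 10, has two neighbouring blocks for asthma.

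- The first is the background condition asthma, with two codes, J45 and J46. J46 has the study name "Severe asthma" in the left column and the ICD-10 label "Status asthmaticus" in the right column.
- The second is headed "Asthma exacerbation" and has five codes: J45.21 ("Mild intermittent asthma with (acute) exacerbation"), J45.31 ("Mild persistent asthma with (acute) exacerbation"), J45.41 ("Moderate persistent asthma with (acute) exacerbation"), J45.51 ("Severe persistent asthma with (acute) exacerbation") and J45.91 (the same for asthma of unspecified grade). J46 is not among them.

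The Amendments and Updates table gives the reason for revising these codes in version 2.0: "additional codes have been found to clarify and expand the definition of asthma exacerbation". Its item 3 says that asthma exacerbations are examined in patients who have had such an exacerbation before. The note under Table 10 leaves only the ICD-9 codes to the SAP.

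**The concern.** The J46 row does not agree with itself. Its ICD-10 label names an acute event, while its study name describes a standing condition, and the table follows the study name. The code that stands for a severe acute attack therefore contributes to the asthma comorbidity flag but not to the exacerbation count, and no reason is given.

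Two uses are exposed. In follow-up, an attack coded only J46 produces no exacerbation event. In the history, a patient whose past attacks were coded only J46 appears as a patient with asthma and no prior exacerbation, and so would fall outside a population defined by prior exacerbation. Both omissions lie at the severe end, where an exacerbation outcome should be least open to doubt.

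**Working it through.** The document gives no figure to reproduce. The check compares code sets and then follows the consequence.

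**Step 1: the two lists in Table 10.**

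| Table 10 block | Codes | J46 included? |
|---|---|---|
| Asthma (background) | J45, J46 | Yes |
| Asthma exacerbation | J45.21, J45.31, J45.41, J45.51, J45.91 | No |

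All five exacerbation codes are subcodes of J45. A record carrying J46 and none of these five matches nothing in the second list. A record carrying J46 together with one of the five still matches. The loss is therefore confined to attacks coded J46 only. J46 appears nowhere else in the visible text.

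**Step 2: is this left to the SAP?** No. The ICD-10 list is printed in Table 10, and the asthma rows are not redacted. Only ICD-9 is deferred.

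**Step 3: comparison with COPD.** Appendix 5 defines COPD exacerbations by a moderate algorithm based on outpatient visits and a severe algorithm based on inpatient stays, and combines the two. The asthma list has codes for exacerbation at each named grade of asthma, but not the separate code for the severe acute attack. This shows a difference in treatment. It does not show that the asthma definition had to follow the same structure.

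**Step 4: size.** Let s be the share of attacks coded only J46. The document does not give s, so the values below are assumptions. Hold the analysed population fixed.

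- Observed rate = true rate × (1 − s). For s = 0.01, 0.05 and 0.10 the rate is understated by 1%, 5% and 10%.
- Observed rate ratio = true rate ratio × (1 − s in the OM-85 group) / (1 − s in the SOC group).
- If s is equal in the two groups, the factor is 1 and the ratio is unchanged.
- If s is 0.05 with OM-85 and 0.10 with SOC, the factor is 0.95 / 0.90 = 1.056. With the shares reversed it is 0.90 / 0.95 = 0.947.

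The ratio is distorted only if the J46-only share differs between the groups, and then only modestly over this range.

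**Step 5: where such attacks could be recorded.** Footnote 2 to Table 8 (Section 3.3.2.2) says the THIN databases do not cover hospital stays, intensive care or emergency care. Section 3.4.2 describes Inspur as drawing on 82 secondary and tertiary hospitals. Severe attacks are therefore more likely to appear in the Chinese data than in the Belgian or Italian data.

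**The case against.** The strongest reply is that the outcome definition cannot be seen in full. Asthma exacerbation appears in no primary or secondary objective. It can belong only to the exploratory objectives, whose wording, populations and Table 8 definitions are redacted, and a further code named there cannot be excluded. The only visible statement about prior exacerbations is an amendment-log entry. This stands, and the point is therefore limited to the visible code list.

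It also stands that the five listed codes already cover exacerbation at every named grade of asthma, severe persistent included, and that attacks with both kinds of code are counted. A reader might infer that the most severe attacks as a group go uncounted. The table supports only the narrower statement about attacks coded J46 alone.

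A reader might also notice that the five exacerbation codes are longer than the other visible entries, and infer that they would fail to match in a source that stores shorter codes, leaving J46 as the main acute code. No section says at what depth any source stores asthma codes, and listing other diseases by whole category says nothing about storage. The documents do not support that inference, or any restriction or withholding of a country's result on that ground.

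Finally, the amendment log does not promise J46 or claim a complete list, so there is no contradiction with it. It shows only that the purpose was to widen the definition. What the reply does not answer is the J46 row itself: an acute-event code filed under a chronic label, in a list the protocol fixes.

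**Conclusion.** The point holds in a limited form, and its severity is minor. On the visible ICD-10 list, attacks coded only J46 are left out of the exacerbation count, and patients with only such attacks in their history are not recognised as having had an exacerbation. This rests on two assumptions: that status asthmaticus has its ordinary meaning of an acute severe attack, which the protocol does not itself state, and that the redacted exploratory definitions add no further code.

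The size is unknown and may be small. The effect probably falls mainly on Inspur. A reader might infer that the effectiveness conclusions are at risk, but the documents do not support that: the primary outcome is the rate of RTI episodes, asthma exacerbation is not among the listed secondary outcomes, and the asthma comorbidity already includes J46.

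**What to change.** In Table 10, add J46 to the asthma exacerbation list and apply it to both the follow-up outcome and the prior-exacerbation criterion. Keep J46 in the background asthma definition as well, because the two uses do not conflict. Change its study name so that it agrees with the ICD-10 label. Make the same choice when the ICD-9 list is written in the SAP, since Section 3.3 says Italy uses both revisions. If the sponsor intends J46 to count as background disease only, the table should say so and give the reason.

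The cost is one added code line and one corrected label, with the matching ICD-9 entry. No other definition or analysis needs to change.
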